11.5 Summary of Efficacy Analyses

Endpoint	Analysis	Populations
Proportion of subjects with improved acne scars and marks at week 4 of treatment (Visit 3) and, at the same time, without any new facial acne scars with respect to baseline (Visit 1).	Exact binomial test	FAS PP
Proportion of subjects with improved acne scars and marks at week 2 and 8 of treatment (Visits 2 and 4) and, at the same time, without any new facial acne scars with respect to baseline (Visit 1).	Exact binomial test	FAS
Proportion of subjects at week 2, 4 and 8 of treatment, without any new facial acne lesions with respect to baseline (Visit 1).	Exact binomial test	FAS
Change from baseline (Visit 1) to each time point (Visit 2, 3 and 4) in the acne severity, according to the Investigator Global Assessment.	Wilcoxon signed rank- sum test	FAS
Change from baseline (Visit 1) to each time point (Visit 2, 3 and 4) in the skin roughness, on a 4-point scale from 0 (none; very smooth) to 3 (severe; very rough).	Wilcoxon signed rank- sum test	FAS
Change from baseline (Visit 1) to each time point (Visit 2, 3 and 4) in the skin texture on a 6-point scale from 0 (worse) to 5 (complete improvement).	Number (N) and the proportion of subjects (%) for each item	FAS
Subject's and Investigator's global evaluation on performance of the study product at the end of the study (Visit 4) by means of a 7-items scale.	Number (N) and the proportion of subjects (%) for each item	FAS
Subject's overall acceptability of the treatment at the end of the study (Visit 4) by means of a 5-item scale.	Number (N) and the proportion of subjects (%) for each item	FAS

Subject's adherence to treatment by the product accountability.	Mean percentage within each treatment group	FAS
---	---	-----

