5.2 Secondary Objectives and Endpoints

The secondary objectives of this clinical investigation are:

- To evaluate the performance of PAPIX ACNE SCAR in the prevention and improvement of acne scars after 2 and 8 weeks of treatment. This endpoint will be assessed as the proportion of subjects with improved acne scars and marks with respect to baseline and, at the same time, without any new facial acne scars after 2 and 8 weeks of treatment. The improvement of acne scars and marks will be assessed as the change in the qualitative Scar Global Assessment (SGA) by Goodman and Baron (2006) [26] between baseline and Week 2 and 8. The number of acne scars, to identify any new scars, will be assessed through the scars count and comparison with baseline.
- To evaluate the performance of PAPIX ACNE SCAR in the prevention of acne lesions after 2, 4 and 8 weeks of treatment. The number of acne lesions, to identify any new lesions, will be assessed through the lesions count and comparison with baseline.
- To evaluate the improvement in acne severity after 2, 4 and 8 weeks of treatment, through the Investigator Global Assessment, ranging from 0 (clear; clear skin with no lesions) to 4 (severe; many inflammatory and non-inflammatory lesions).
- To evaluate the improvement of the skin roughness on a 4-point scale from 0 (none; very smooth) to 3 (severe; very rough) after 2, 4 and 8 weeks of treatment.
- To evaluate the improvement of the skin texture on a 6-point scale from 0 (worse) to 5 (complete improvement), after 2, 4 and 8 weeks of treatment.
- To evaluate the subject's adherence to treatment by the product accountability and information asked to the subject.
- To evaluate the subject's and Investigator's global evaluation of satisfaction with regards to the performance of PAPIX ACNE SCAR, through a specific questionnaire.
- To evaluate the subject's overall acceptability of the treatment, through a specific questionnaire.

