7.3.5.2 Secondary endpoints

The prevention and improvement of acne scars after 2 and 8 weeks of treatment will be assessed as the difference from baseline and analysed using paired t-test. The number of new scars will be assessed by count and comparison with baseline. The improvement of acne scars and marks will be assessed as the change of at least one grade in the qualitative Scar Global Assessment (SGA) by Goodman and Baron [26] between baseline and Week 2 and 8.

The number of new lesions will be assessed by count after 2 and 8 weeks and comparison with baseline.

Acne severity after 2, 4 and 8 weeks of treatment will be assessed through the IGA. Changes from baseline will be compared using Wilcoxon signed rank-sum test.

The improvement of skin roughness will be assessed on a 4-point scale from 0 (none; very smooth) to 3 (severe; very rough). Changes from baseline will be compared using Wilcoxon signed rank-sum test.

Skin texture change will be assessed on a 6-point scale from 0 (worse) to 5 (complete improvement), after 2, 4 and 8 weeks of treatment and it will be summarized through the number (N) and the proportion of patients (%) for each item.

The number of applications will be self-reported by the subject and the product accountability will be summarized to assess adherence to treatment.

Subject's and Investigator's global evaluation on performance of the study product obtained at the end of the study (Visit 4) by means of a 7-items scale will be summarized through number (N) and proportion of patients (%) for each item.

Subject's evaluation of overall acceptability with treatment, obtained by means of a 5-item scale will be summarized through number (N) and the proportion of patients (%) for each item.

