9.1.3 Treatment Compliance

The Investigator was responsible for ensuring the accountability of the study product.

The Investigator should maintain records that adequately documented:

- that the subjects were provided with the quantities specified by the clinical investigation plan/amendment(s)
- that all study products provided by the Sponsor were fully reconciled.

The investigator visually checked the used/unused tubes of study product returned by the subjects at study visit. In order to quantify the compliance to the treatment the Investigator also asked to the subject if the product was used according to the instructions and how many times the treatment was skipped (if any). The subject will be considered compliant to the treatment if the number of skipped applications is not exceeding 20% of the expected applications.

In the Listing 16.2.5, both accountability of returned product and adherence to treatment reported by the subject will be described.

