11.3 Measurements of Treatment Compliance

Treatment compliance will be assessed through the counting of the number of applications performed. The following formula will be used:

 $\frac{Number of applications performed}{Number of applications planned} * 100$

The number of planned applications will be estimated on the basis of the treatment duration x 2 times.

Treatment compliance will be estimated separately for the two study periods: Visit 1 - Visit 3 and Visit 3 - Visit 4 and it will be described in the Listing 16.2.5.

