11.4.2 Secondary Efficacy Endpoints

The proportion of subjects with acne scars and marks improved with respect to baseline and, at the same time, without any new facial acne scars after 2 and 8 weeks of treatment (treatment success) will be described using number (N) and percentage (%). The improvement of acne scars and marks will be assessed as the change of at least one grade in the qualitative Scar Global Assessment (SGA) by Goodman and Baron between baseline and Week 2 and 8. The number of new acne scars will be assessed by count after 2 and 8 weeks and comparison with baseline. The proportion of treatment successes will be compared to a referent proportion (50%, Null hypothesis proportion) using the exact binomial test.

The proportion of subjects at week 2, 4 and 8 of treatment, without any new facial acne lesions with respect to baseline (Visit 1) will be described using number (N) and percentage (%); the proportion of treatment successes will be compared to a referent proportion (50%, Null hypothesis proportion) using the exact binomial test.

Acne severity after 2, 4 and 8 weeks of treatment will be assessed through the IGA. Changes from baseline will be compared using Wilcoxon signed rank-sum test.

The improvement of skin roughness will be assessed on a 4-point scale from 0 (none; very smooth) to 3 (severe; very rough). Changes from baseline will be compared using Wilcoxon signed rank-sum test.

Skin texture change will be assessed on a 6-point scale from 0 (worse) to 5 (complete improvement), after 2, 4 and 8 weeks of treatment and it will be summarized through the number (N) and the proportion of subjects (%) for each item.

The number of applications will be self-reported by the subject to assess adherence to treatment.

Subject's and Investigator's global evaluation on performance of the study product obtained at the end of the study (Visit 4) by means of a 7-items scale will be summarized through number (N) and proportion of subjects (%) for each item.

Subject's evaluation of overall acceptability with treatment, obtained by means of a 5-item scale will be summarized through number (N) and the proportion of subjects (%) for each item.

The secondary endpoints will be described from Table 14.2.2.1 to Table 14.2.2.8.

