13. DEVIATIONS FROM THE PROTOCOL SPECIFIED ANALYSIS

No deviation from the analyses specified in the study protocol have been included in this Statistical Analysis Plan (SAP).

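### The adherence table titled as product accountability would hold a self-reported percentage, and the accountability summary that the protocol specifies is missing from the SAP

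*SAP*

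**What the plan says.** **Protocol.** The secondary objective in 5.2 rests on two sources: "adherence to treatment by the product accountability and information asked to the subject". The analysis text in 7.3.5.2, repeated in the synopsis, also has two parts: "The number of applications will be self-reported by the subject and the product accountability will be summarized to assess adherence to treatment". The endpoint list in the synopsis names accountability alone.

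**SAP.** Objective 8 in SAP 3.2 keeps both sources. The endpoint in SAP 5.2, its row in SAP 11.5 and the title of Table 14.2.2.8 name accountability only; the row reads "adherence to treatment by the product accountability" and its statistic is a mean percentage in the FAS. The analysis text in SAP 11.4.2 reads: "The number of applications will be self-reported by the subject to assess adherence to treatment". SAP 11.3 gives the formula: "Treatment compliance will be assessed through the counting of the number of applications performed", divided by the planned number. SAP 9.1.3 says that returned tubes were inspected by eye, that subjects were asked about skipped treatments, and that both kinds of information go into Listing 16.2.5. SAP 13 states: "No deviation from the analyses specified in the study protocol have been included".

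**The concern.** The title of Table 14.2.2.8 tells the reader that adherence was measured from product dispensed and returned. The plan behind it produces a figure from subjects' recall. In an open-label, single-arm study these are different kinds of evidence, and a reader of the report could not tell from the table which one is shown.

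The SAP sentence on adherence is also the protocol sentence without its accountability clause. A summary that the protocol specifies has therefore gone, while the section meant to record such changes says that there are none.

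**Working it through.** The SAP gives no adherence result to reproduce, so the check is a comparison of texts plus the little arithmetic that the percentage needs.

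**Step 1: which data feed the percentage?**
- Formula (SAP 11.3): 100 × applications performed / applications planned.
- Denominator (SAP 11.3): "The number of planned applications will be estimated on the basis of the treatment duration x 2 times". At 56 days this is 56 × 2 = 112. At the limits of the Visit 4 window it is 53 × 2 = 106 and 59 × 2 = 118.
- Numerator: SAP 11.3 names no source. SAP 11.4.2 says the count is self-reported. SAP 9.1.3 says the subject was asked about skipped treatments. The variable table in SAP 9.1 has two adherence variables, ecoccur (compliance) and ecdur (times treatment was skipped). No variable is defined for tubes or for amount of gel, dispensed or returned.
- Compliance rule (SAP 9.1.3): skipped applications at most 20% of those expected. 0.20 × 112 = 22.4, so at most 22 at 56 days. 0.20 × 106 = 21.2, so 21 at 53 days. 0.20 × 118 = 23.6, so 23 at 59 days.

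Every quantity comes from treatment duration and self-report. That the numerator equals planned minus reported skips is an inference, but the SAP offers no other route.

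**Step 2: protocol against SAP**

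| Element | Protocol | SAP |
|---|---|---|
| Objective | Accountability and subject's information (5.2) | The same two sources (3.2) |
| Endpoint label | Accountability (synopsis) | Accountability (5.2, 11.5, Table 14.2.2.8) |
| Analysis: self-report | Yes (7.3.5.2) | Yes (11.4.2) |
| Analysis: accountability summary | Yes (7.3.5.2) | None; Listing 16.2.5 only |
| Deviation declared | – | None (13) |

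The label and the analysis part company in the SAP, and the accountability summary is the element that is lost.

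**Step 3: can the missing summary be supplied?** Protocol 6.2.1.4 and section 11 require records of tubes delivered to and returned by each subject. The flow-chart has dispensing at Visits 1 and 3 and returns at Visits 3 and 4, which matches the two compliance periods in SAP 11.3. Counts of tubes dispensed and returned should therefore exist at site. Whether returned tubes were classed as empty, part-used or unopened is not shown, since the documents describe only a visual check.

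**Step 4: could tube counts be read as adherence?** Not on these documents. Six tubes of 7 ml (Protocol 6.2.1.1) are 42 ml, and 42 / 112 = 0.375 ml per planned application. Protocol 6.2.1.2 confines application to the lesions where possible; Protocol 6.4.1 gives 2 finger-tip units on the face each time. No volume per finger-tip unit is stated, so whether six tubes exceed or fall short of full use cannot be determined.

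**The case against.** Several points on the other side have weight.

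- **Accountability is not lost.** Listing 16.2.5 shows it beside self-report, and with 40 subjects enrolled, all at one site (SAP 7 and 9.2), a reader can go through it. This stands as far as it goes, but a listing of individual subjects is not the summary that the protocol specifies.
- **The table list is open-ended.** SAP 14 allows additional tables. That permits a summary; it does not plan one, and it does not correct the title.
- **Self-report is legitimate.** The protocol specifies it. This stands in full: the fault lies in the label and the missing summary, not in asking the subject.
- **The numerator's source is inferred.** True. If tube data were meant to enter the percentage, the SAP would need a variable and a formula for them, and it has neither.

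A reader might infer more: that each unopened tube returned is 1/6 = 16.7% of use, so that two (2/6 = 33%) would contradict a report of at most 20% skipped. The documents do not support this. It compares a share of supply with a share of applications, and it needs six tubes to equal full use, which is not established. If gel goes only on lesions, a fully adherent subject with few lesions could return unopened tubes. For the same reason no rule for counting contradictory subjects can be derived. Nor do the documents say that self-report overstates adherence in this trial.

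**Conclusion.** The point holds as a mismatch between label and content, an omitted protocol-specified summary, and an inaccurate statement in SAP 13. It is an error in the plan as written rather than a missing detail, because following the SAP literally gives a self-reported percentage under an accountability title.

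Its size is small: one secondary endpoint and one table, described without a test. The primary exact binomial test, its error rate and the sample size do not depend on it. No numerical bias in the adherence figure can be estimated from the documents, and none is claimed.

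The conclusion rests on one inference, that the count of applications performed comes from reported skips, which SAP 9.1, 9.1.3 and 11.4.2 together support.

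**What to change.** 1. In SAP 11.5 and Table 14.2.2.8, label the percentage as self-reported adherence, and state in SAP 11.3 where the numerator comes from.
2. Restore the accountability summary in the same table: tubes dispensed and tubes returned per subject, for Visit 1 to Visit 3 and for Visit 3 to Visit 4, from the records required by Protocol 6.2.1.4 and section 11. Use only counts or categories that were actually recorded.
3. If the tube data cannot be summarised, say so in SAP 13 as a departure from Protocol 7.3.5.2.
4. Present the tube block as accountability, not as a second adherence rate. Protocol 6.2.1.2 and 6.4.1 differ on where and how much gel is applied and must be reconciled before tube use can be interpreted as adherence.

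The cost is a few words of SAP text and one small table block. If the site's tube records are not yet in the database, entering them for the enrolled subjects is additional work.

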12. SAFETY EVALUATION

12.1 Extent of Exposure

The extent of exposure is of 8 weeks (56 days \pm 3).

12.2 Adverse Events

All enrolled subjects receiving at least one treatment application will be included in the safety analysis. The safety analysis will include Deaths, Serious Adverse Events and other significant Adverse Events.

Adverse events (AEs) and Adverse Device Events (ADEs) will be coded using the last updated version of the Medical Dictionary for Regulatory Activities (MedDRA) to give a preferred term (PT) and a system/organ class term (SOC) for each event. The number of subjects who experienced at least one AE or ADE, study product-related AE or ADE, serious AE or ADE, severe AE or ADE and the number of subjects withdrawn due to AE will be summarized in the Table 14.3.1.

For each SOC and preferred term, summaries will be made with respect to the proportion of subjects having at least one occurrence of that event during the study and the total number of events. The incidence of AEs and ADEs will be presented overall, by SOC and preferred term, and additional grouping by severity and relationship to the study treatment in the Table 14.3.2.

12.3 Other safety endpoints

Local tolerability at the site of administration (e.g. skin increased itching or redness or irritation) will be reported and summarized in the Table 14.3.3 and in the Listing 16.2.8.

13. DEVIATIONS FROM THE PROTOCOL SPECIFIED ANALYSIS

No deviation from the analyses specified in the study protocol have been included in this Statistical Analysis Plan (SAP).

14. LIST AND SAMPLES OF TABLES, FIGURES AND GRAPHS

The following lists of tables might not be exhaustive. Additional tables can be produced if necessary.

14.1 Demographic data

Table 14.1.1 Subjects' disposition

Table 14.1.2 Protocol deviations

Table 14.1.3 Demographic characteristics

Table 14.1.4 Disease details at baseline

Table 14.1.5 Medical history

Table 14.1.6 Surgical history

Table 14.1.7 Physical examination

14.2 Efficacy data

14.2.1 Primary endpoints

Table 14.2.1.1 Proportion of subjects with improved acne scars and marks at week 4 of treatment (Visit 3) and, at the same time, without any new facial acne scars with respect to baseline (Visit 1) (FAS Population)

Table 14.2.1.2 Proportion of subjects with improved acne scars and marks at week 4 of treatment (Visit 3) and, at the same time, without any new facial acne scars with respect to baseline (Visit 1) (PP Population)

14.2.2 Secondary endpoints

Table 14.2.2.1 Proportion of subjects with improved acne scars and marks at week 2 and 8 of treatment (Visits 2 and 4) and, at the same time, without any new facial acne scars with respect to baseline (Visit 1) (FAS Population)

Table 14.2.2.2 Proportion of subjects at week 2, 4 and 8 of treatment, without any new facial acne lesions with respect to baseline (Visit 1) (FAS Population)

Table 14.2.2.3 Change from baseline (Visit 1) to each time point (Visit 2, 3 and 4) in the acne severity, according to the Investigator Global Assessment (FAS Population)

Table 14.2.2.4 Change from baseline (Visit 1) to each time point (Visit 2, 3 and 4) in the skin roughness on a 4-point scale (FAS Population)

Table 14.2.2.5 Change from baseline (Visit 1) to each time point (Visit 2, 3 and 4) in the skin texture on a 6-point scale (FAS Population)

Table 14.2.2.6 Subject's and Investigator's global evaluation on performance of the study product at the end of the study (Visit 4) by means of a 7-items scale (FAS Population)

Table 14.2.2.7 Subject's overall acceptability of the treatment at the end of the study (Visit 4) by means of a 5item scale (FAS Population)

Table 14.2.2.8 Subject's adherence to treatment by the product accountability (FAS Population)

14.3 Safety data

Table 14.3.1 Analysis of adverse events observed (Safety population)

Table 14.3.2 Display of adverse events observed (Safety population)

Table 14.3.3 Subject's local tolerability of study product at the site of administration (Safety population)

14.4 Sample tables

Tables reporting statistical analysis will be issued as PDF files. Mock samples are reported in the following sections.

14.4.1 Sample summary table

	. Bable .xx.x.x 	*******
Characteristic	Statistic	PAPER ACHE SCAR
SAH L	Class A	an (an. ab)
	Class B	MR (MR.85)
VAR 2	11	
	Mean (ED)	MELES (MELES)
	Median	38.85
	ИЦл — Изан	RE-RE / RE-RE
WAR 3	Class A	NX (NX.X5)
	Class B	RE (RE, 83)
	Class C	R.H. (1021.1 R.N.)
	Class D	an (m e.)
VAR-4	¥	1 1 1 1 KE (1 1 1 1
	Mean (SD)	KAR.AR (R.AR)
	Median	00008 J 2000
	Min - Man	ana.au / aux.s
VAB 5		3.8
	Hean (ED)	MR. MN (RN. MM)
	Median	REINE
	Min + Mass	RH - XH - F - RHH - HH
VAR E	The second second	8.8
	Mean (ED)	nn.ns (n.ss)
	Median	BR.MR
	Hin + Mas	term a sector of the rectangulater

14.4.2 Sample table for efficacy analysis – continuous variables

Table mx.3.2.8 Summary and Analysis of Population)							
Endpoint	Statistic	PAPIX ACHE SCAR					
Visit 1 (Baseline)	8.37 ST	EX.M					
	Nean (SD)	-R.N. 48.883					
	Madaan	-10., post					
	Min - Max	-s.ss / s.ss					
Visit 2	w	ALC: NO.					
	Main (SD)	-a(aa.)					
	Median.	- N M.N					
	Milin - Max	-a. KR / N. KR					
	p-value	8.5 BOD					
Visit 3	84	NOV 20					
	66m=11 (322)	-R.SE (R.SE)					
	Med Lan	+ 8.308					
	Min - Max	-R. KR / R. KR					
	g=yalue	8.300					
Visit 4 (End of study)	86 (8:8:8					
	Mast (SD)	-10.100 (0.100)					
	Madlan	-8.388					
	stile - Mass	-a.kk / K.KA					
	p-value.	b., stars					

Statistical significance: * p+0.05; ** p+0.01; *** p+0.801. CONFIDENTIAL

Program: TANKANANA ANA.gas

Date: HEXXXXXXXX

14.4.3 Sample table for efficacy analysis – discrete variables

Span	 						
Frot	1.1	Real	01/7	BV	PAS	-Aon/0	0

Page 1 of a

them.	Table %8:8:8:8 ary and Analysis of f Population)	
Characteristic	Statistic	PAPER ACHE BOAR
Visit 1 (Baseline)	Class A	as (as sh)
	Class B	RE & REAL
Viait 2	Class &	as (ax. 25)
	Class B	MR (MR. 85)
	p-value	8.888
Visit 3	Class &	RE (RE. 85)
	Class B	300 f 300-010
	p-value	8.888
Visit 6 (End of study)	Class A	NE (NE. 84)
there a from as arough)	Class B	
	p-value	88 (88.85) N.800

Statistical significance: * p+0.05; ** p+0.01; *** p+0.001.

Program: TREEXAREN ARE.see CONFIDENTIAL

Date: REXXXXER

14.4.4 Sample table for adverse events analysis

	Table MR.K.N.M Adverse Events (Safety Population)	
AE details	Htat 19110	PAPIN ACME SCAR
Have any AE occurred?	ND	a (38.41)
	AET	a (a
Total number of adverse events*	8	(5)-222)
Relatedness with study treatment	Certelp.	x (xx.x5)
	Probable	at (hat.att)
	Fossible	38 (BRLED)
	Doubtrol	a (ss.sh)
	Bone	N (38.35)
	The landsome	
Severity	Mild	x (xx,xh)
	Modezate	a (as.sh)
	Devare	a (ss.s5)
Sericummen	TER	00 (NALNY)
	6453	a (1 ma.ab)

" More than one adverse event per patient.

Statistical significances * pc0.05; ** pc0.01; *** pc0.001. Note: p-values from a shi-square test for discrete variables and T-test for continuous variables.

Programa TERRENERS SER. DOB CONFIDENTIAL

Date: REXEXERN

